8.1.5 TREATMENT RESPONSE TO ZINFORO® IN PATIENTS WITH CAP

Table 22. Response to Zinforo treatment in patients with CAP

Treatment response	All CAP patients (N=XX)	
	n	%
Zinforo treatment response		
Clinical response		
Clinical failure		
Time to clinical response		
Mean (SD)		
Median (Min-Max)		
Unknown		
Zinforo early treatment response		
Response ≤4 days		
Response >4 days		
No response		
Unknown		
Clinical cure achieved		
Yes		
No		
Time to clinical cure		
Mean (SD)		
Median (Min-Max)		
Unknown		
Clinical stability achieved		
Time to clinical stability		
Mean (SD)		
Median (Min-Max)		
Unknown		
Clinical improvement achieved		
Time to clinical improvement		
Mean (SD)		
Median (Min-Max)		
Unknown		

Abbreviations: Max: maximum; Min: minimum; SD: standard deviation.

PFIZER CONFIDENTIAL

CCI

8.1.6 ADDITIONAL CLINICAL OUTCOMES IN PATIENTS WITH CAP

Table 23. Additional clinical outcomes in response to Zinforo treatment in patients with CAP

Additional clinical outcomes	All CAP patients (N=XX)	
	n	%
Discharge status		
Died in the hospital		
Discharged to a nursing home or extended care facility		
Discharged to independent living (with or without support)		
Other		
Unknown		
Vital status at end of follow up		
Patient is still alive		
Patient is deceased		
If deceased		
Duration of days from discharge until death(days)		
Mean (SD)		
Median (Min-Max)		
Unknown		
Minimum inhibitory concentrations (MIC) of antibacterial drugs assessed		
Yes		
No		
Unknown		
If assessed		
Day of assessment since index hospitalization		
Mean (SD)		
Median (Min-Max)		
MIC of ceftaroline for all isolated pathogens		
MIC of oxacillin, vancomycin, linezolid, and daptomycin for S. aureus		
MIC of ceftriaxone for MSSA		
MIC of penicillin and ceftriaxone for S. pneumonia		

Abbreviations: Max: maximum; MIC: minimum inhibitory concentrations; Min: minimum; SD: standard deviation.

8.1.7 TREATMENT MODIFICATIONS / ADVERSE EVENTS IN PATIENTS WITH CAP

Table 24. Clinical failure with Zinforo in patients with CAP

Clinical failure with Zinforo	All CAP patients (N=XX)	
	n	%
Etiology of clinical failure		
Failure related to CAP		
Failure unrelated to CAP		
Unknown		
Reason for clinical failure		
Treatment modification due to AE		
Time to modification (days)		
Mean (SD)		
Median (Min-Max)		
Unknown		
Drug-drug interaction		
Insufficient response		
Death due to index infection		
Time to death due to infection (days)		
Mean (SD)		
Median (Min-Max)		
Unknown		
Death due to other		
Relapse or recurrence		
Time to relapse/recurrence:		
Mean (SD)		
Median (Min-Max)		
Unknown		

Abbreviations: AE: adverse events; Max: maximum; Min: minimum; SD: standard deviation.

PFIZER CONFIDENTIAL

CCI

Table 25. Clinical failure with Zinforo due to adverse events in patients with CAP

Clinical failure to Zinforo due to AEs	All CAP patients (N=XX)
	n %
AE causing Zinforo discontinuation	
Infections and infestations	
Clostridium difficile colitis	
Other	
Blood and lymphatic system disorders	
Activated partial thromboplastin time (aPTT) prolonged	
Agranulocytosis	
Anaemia	
Eosinophilia	
International normalized ratio (INR) increased	
Leucopenia	
Neutropenia	
Prothrombin time (PT) prolonged	
Thrombocytopenia	
Other	
Immune system disorders	
Anaphylaxis	
Hypersensitivity (e.g. urticarial, lip and face swelling)	
Pruritus	
Rash	
Other	
Nervous system disorders	
Dizziness	
Headache	
Other	
Vascular disorders	
Phlebitis	
Other	
Gastrointestinal disorders	
Abdominal pain	
Diarrhea	
Nausea	
Vomiting	
Other	
Hepatobiliary disorders	
Increased transaminases	
Other	
Renal urinary disorders	
Blood creatinine increased	
Other	
General disorders and administrative site conditions	
Infusion site reaction (e.g. erythema, phlebitis, pain)	
Pyrexia	
Other	
Investigations	

PFIZER CONFIDENTIAL

CCI

Clinical failure to Zinforo due to AEs	All CAP patients (N=XX)	
	n	%
Coombs direct test positive		
Other		
Unknown		

Abbreviations: AE: adverse events, aPTT: activated partial thromboplastin time

PFIZER CONFIDENTIAL

CCI

Table 26. Seriousness of adverse events in patients with CAP

Clinical failure to Zinforo	All CAP patients (N=XX)	
	n	%
Serious AE at Zinforo discontinuation		
Yes		
No		
Unknown		
Seriousness criteria applied (for AEs indicated as serious)		
Resulted in death		
Life-threatening		
Hospitalization/prolongation of hospitalization		
Persistent/significant disability/incapacity		
Congenital anomaly/birth defect		
Important medical event		
None of the above		
Unknown		

Abbreviations: AE: adverse event.

PFIZER CONFIDENTIAL

CCI

Table 27. Post Zinforo treatment- Summary across all lines in patients with CAP

Antibiotic treatment post Zinforo	All CAP patients (N=XX)
	n %
Antibiotic treatment received for index infection after Zinforo	
Yes	
No	
Post Zinforo treatment received	
Aminoglycoside	
Betalactam	
Carbapenem	
Ceftriaxone	
Cephalosporins	
Glycopeptide	
Macrolide	
Betalactam	
/Combination	
Quinolone	
Sulfonamide	
Clindamycin	
Linezolid	
Other antibiotic agent	
Unknown	
Line of therapy	
First	
Second	
Third	
Fourth	
Number of post Zinforo lines of therapy	
Mean (SD)	
Median (Min-Max)	
Route of administration	
Oral	
Intra-venous	
Intra-muscular	
Subcutaneous	
Unknown	
Duration from Zinforo discontinuation to initiation of new treatment (days)	
Mean (SD)	
Median (Min-Max)	
Unknown	
Duration of treatment (days)	

PFIZER CONFIDENTIAL

CCI

Antibiotic treatment post Zinforo	All CAP patients (N=XX)
	n %
Mean (SD)	
Median (Min-Max)	
Unknown	
Treatment type	
Empiric	
Definitive/Specific	
Unknown	
Number of administrations	
Mean (SD)	
Median (Min-Max)	
Number of doses administered	
Mean (SD)	
Median (Min-Max)	
Administration location	
ICU	
General ward	
Unknown	
Reason for switch	
Lack of efficacy of previous treatment	
Side effect of previous treatment	
Drug interaction of previous treatment	
Results of susceptibility test/pathogen identification	
Special population with renal impairment	
Other	
Unknown	

Abbreviations: ICU: intensive care unit; Max: maximum; Min: minimum; SD: standard deviation.

Table 28. Response to post-Zinforo treatment in patients with CAP

Post Zinforo treatment response	All CAP patients (N=XX)	
	n	%
Treatment response to post- Zinforo treatment		
Clinical response		
Clinical failure		
Unknown		
Clinical cure achieved		
Yes		
No		
Unknown		
If clinical failure to post-Zinforo treatment		
Treatment modification due to adverse event		
Drug-drug interaction		
Insufficient response		
Relapse/reoccurrence		
Death due to infection		
Death due to other		
Unknown		

PFIZER CONFIDENTIAL

CCI

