8. RESEARCH QUESTION AND OBJECTIVES

Study Aim:

The overall study aim is to provide real world evidence (RWE) on the characteristics, clinical management, treatment outcomes and healthcare resource use of adult patients aged 18 years and older admitted to the hospital for CAP or cSSTI who received Zinforo[®] in a usual care setting in Europe and Latin America on or before 31-May-2019.

Specific Objectives:

- To describe the characteristics of patients hospitalized for CAP or cSSTI who received Zinforo® in a usual care setting in Europe and Latin America on or before 31-May-2019.
- To describe physicians' use of Zinforo® in the clinical management of patients hospitalized for CAP or cSSTI in relation to their use of other antibiotics (first-line vs. second-line/salvage, monotherapy vs. combination therapy, empiric vs. definitive therapy).
- To estimate the proportion of patients hospitalized for CAP or cSSTI who responded to Zinforo® (clinical response defined as no further intravenous (IV) antibiotic, switch to an oral antibiotic, or IV antibiotic treatment streamlining/de-escalation prior to discharge from the hospital).
- To estimate the proportion of patients hospitalized for CAP or cSSTI who had treatment modification of Zinforo® (defined as switch to another IV antibiotic due to an adverse reaction, drug-drug interaction, insufficient response, or a microbiological diagnosis indicating that the pathogen is not susceptible to Zinforo®).
- To describe the clinical outcomes (eg, hospital readmission, mortality) of patients hospitalized for CAP or cSSTI after starting Zinforo® stratified by clinical response.
- To describe the healthcare resource use of patients hospitalized for CAP or cSSTI after starting Zinforo® stratified by clinical response.

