 - Microbiological Diagnosis (investigations or diagnostic tests performed, positive microbiological diagnosis obtained, microorganism name, bacteremia diagnosed, the pathogen(s), source(s), and the specimen collection date(s). Pathogens identified by blood, respiratory (eg, sputum, bronchoalveolar lavage), or pleural effusion cultures will be recorded for patients with bacterial pneumonia. Pathogens identified by blood or skin/soft tissue/bone/wound cultures will be recorded for patients with cSSTIs. Minimum inhibitory concentrations (MIC) of antibacterial drugs for pathogens isolated from samples collected within one week before the start of treatment through 24 hours after discontinuation of Zinforo® will be recorded:
 - MIC of ceftaroline for all isolated pathogens;
 - MIC of oxacillin, vancomycin, linezolid, and daptomycin for *S. aureus*;
 - MIC of ceftriaxone for MSSA;
 - MIC of penicillin and ceftriaxone for *S. pneumoniae*.

- Zinforo® Treatment (treatment duration, line of therapy, time from hospital admission to first dose, time from symptom onset to first dose, empiric vs. definitive therapy, monotherapy vs. combination therapy, dose, number of infusions per day, number of doses administered, ICU vs. general medical ward administration, reason for switch to Zinforo® if not 1st line treatment).
- Pre-Zinforo® IV Antibiotic Treatments for the index infection (each monotherapy/combination antibiotic therapy name, line of therapy, route of administration, duration of treatment, time from admission to first dose, time from symptom onset to first dose, empiric vs. definitive therapy, daily dose, number of doses administered, treatment response, time to treatment modification from initial dose (days), reason for treatment modification, ICU vs. general medical ward administration).
- Concurrent IV antibiotic treatments administered with Zinforo® for index infection (antibiotic therapy name, route of administration, treatment duration, daily dose, number of doses administered).
- Post-Zinforo® antibiotic treatments for index infection (antibiotic therapy name, route of administration, treatment duration, daily dose, number of doses administered, reason for switch, treatment response, ICU vs. general medical ward administration).

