2.1.4 STUDY OBJECTIVES

The overall study aim of this study is to provide real world evidence (RWE) on the characteristics, clinical management, treatment outcomes and healthcare resource use of adult patients aged 18 years and older admitted to the hospital for CAP or cSSTI who received Zinforo® in a usual care setting in Europe and Latin America on or before 31-May-2019.

Specific objectives of this study are to analyze for the CAP and cSSTI cohorts:

- Objective 1 “Patient characteristics”: To describe the characteristics of patients hospitalized for CAP or cSSTI who received Zinforo® in a usual care setting in Europe and Latin America on or before 31-May-2019
- Objective 2 “Use of Zinforo”: To describe physicians’ use of Zinforo® in the clinical management of patients hospitalized for CAP or cSSTI in relation to their use of other antibiotics (first-line vs. second-line/salvage, monotherapy vs. combination therapy, empiric vs. definitive therapy)
- Objective 3 “Clinical response”: To estimate the proportion of patients hospitalized for CAP or cSSTI who responded to Zinforo® (clinical response defined as no further intravenous (IV) antibiotic, switch to an oral antibiotic, or IV antibiotic treatment streamlining/de-escalation prior to discharge from the hospital);
- Objectives 4 “Additional clinical outcomes”: To describe the clinical outcomes (eg, hospital readmission, mortality) of patients hospitalized for CAP or cSSTI after starting Zinforo® stratified by clinical response;
- Objective 5 “Treatment modification”: To estimate the proportion of patients hospitalized for CAP or cSSTI who had treatment modification of Zinforo® (defined as switch to another IV antibiotic due to an adverse reaction, drug-drug interaction, insufficient response or a microbiological diagnosis indicating that the pathogen is not susceptible to Zinforo®)
- Objective 6 “Healthcare resource use”: To describe the healthcare resource use of patients hospitalized for CAP or cSSTI after starting Zinforo® stratified by clinical response.

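### SAP Tables 28 and 55 pool response to the next antibiotic over Zinforo responders and patients switched after failure or modification, so the percentage depends on case mix

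*SAP*

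**What the plan says.** Objective 3 (SAP 2.1.4; same definition in Protocol section 8) has "clinical response defined as no further intravenous (IV) antibiotic, switch to an oral antibiotic, or IV antibiotic treatment streamlining/de-escalation". A patient moved to an oral or narrower antibiotic is therefore a Zinforo responder who goes on to a further antibiotic. Objective 5 treats the unfavourable switch separately: treatment modification is "defined as switch to another IV antibiotic due to an adverse reaction, drug-drug interaction, insufficient response or a microbiological diagnosis" showing non-susceptibility.

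Both kinds of course enter the post-Zinforo tables. Table 27 (SAP 8.1.7) opens with "Antibiotic treatment received for index infection after Zinforo" and lists oral among the routes. Protocol 9.3 collects "Post-Zinforo® antibiotic treatments for index infection (antibiotic therapy name, route of administration" and more, without the IV restriction that it places on pre-Zinforo treatments. The Table 27 reasons for switch begin with "Lack of efficacy of previous treatment" and continue with side effect, interaction, "Results of susceptibility test/pathogen identification", renal impairment, other and unknown. None is improvement, step-down or de-escalation. Table 54 (SAP 8.1.14) repeats the list for cSSTI.

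Tables 28 and 55 then give "Treatment response to post- Zinforo treatment", cure and failure reason in one all-patients column each. Table numbers here are those on the shells; the SAP's list of tables shows Tables 54 and 55 as 56 and 57.

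**The concern.** Response to post-Zinforo treatment and cure on it are listed endpoints (SAP 5.1.7), so these tables will be produced and read. A patient stepped down after responding and a patient switched because Zinforo failed start the next antibiotic from opposite positions. Averaging them gives a figure that reflects mainly how many of each were in the sample. If step-down patients do better, as one would expect, a reader who takes the figure as response after Zinforo failure will be too optimistic.

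The denominator adds a second ambiguity. Table 27 separates patients who did and did not receive a further antibiotic. Tables 28 and 55 carry the whole-cohort N and offer only an unknown row, so the shell does not say where patients with no further antibiotic go.

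**Working it through.** The plan states no figure for this endpoint, and the study is descriptive (SAP section 3), so there is nothing to reproduce. The check has three parts.

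**1. Does any other section assign a split?**
- SAP 7.1.4 stratifies additional clinical outcomes and resource use by clinical response. It says only that post-Zinforo treatment will be summarised.
- SAP 4.1.4 allows certain unnamed outcomes to be stratified by early response, which has a no-response level (SAP 5.1.2), or by line of treatment. It does not name Tables 28 or 55.
- The reason-for-switch list does not separate the groups. Step-down has no level of its own. The susceptibility level can hold both narrowing after a culture result and a non-susceptible pathogen.

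So no text attaches a split to these tables.

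**2. How far can case mix move the pooled figure?** Let w be the step-down share of post-Zinforo courses, and r the response after failure or modification. Step-down response is assumed to be 95%, and r is assumed to lie between 50% and 70%.

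Pooled = w × 0.95 + (1 − w) × r

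| r | w = 20% | w = 50% | w = 80% |
|---|---|---|---|
| 50% | 59.0% | 72.5% | 86.0% |
| 60% | 67.0% | 77.5% | 88.0% |
| 70% | 75.0% | 82.5% | 90.0% |

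For example, at r = 60% and w = 20%: 0.2 × 0.95 + 0.8 × 0.60 = 0.67. With r fixed at 60%, case mix alone moves the figure by 88 − 67 = 21 points.

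In reverse, r = (pooled − w × 0.95) / (1 − w). A reported 80% is compatible with r = 73.6% at w = 30%, 65% at w = 50%, 45% at w = 70% and 20% at w = 80%.

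**3. How large would the second column be?** The only success proportions in the documents are those of the earlier US chart review (Protocol section 7): 316/398 = 79.4% for pneumonia and 550/647 = 85.0% for skin infection. The total is about 600; its division between cohorts is not given and is assumed below. Expected non-responders = n × (1 − success).

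| CAP / cSSTI | CAP non-responders | cSSTI non-responders |
|---|---|---|
| 200 / 400 | 41.2 | 60.0 |
| 300 / 300 | 61.8 | 45.0 |
| 400 / 200 | 82.4 | 30.0 |

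Not every non-responder receives another antibiotic. If 80% do (assumed), the smallest cell becomes 30.0 × 0.8 = 24, below the stratum minimum of 30 in SAP 4.1.4.

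**The case against.** The strongest reply is that the two groups can be told apart from data already planned: the yes/no Zinforo response item and failure reasons (SAP 5.1.2), modification reasons (SAP 5.1.4), the route of each later drug (SAP 5.1.7), and oral switch and de-escalation (Protocol 9.3). This stands. A reader might infer from the shells that post-Zinforo response can never be interpreted, or that step-down courses are lost in the other category. The documents do not support that. The eCRF is not shown, free text is permitted where needed (Protocol 9.6), and a cross-tabulation with Zinforo response should need no new item. The defect is in the layout, not necessarily in the data collected.

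It is also fair that no objective asks how patients did after Zinforo failed, and that Tables 28 and 55 are not labelled as rescue results. That limits the importance of the point, but it does not make a mixed percentage informative for a listed endpoint.

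Finally, the 30-patient rule could suppress a split, and a late eCRF change could mean going back to charts already abstracted. Both bear on how to make the fix. Neither is a reason to leave the tables pooled.

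**Conclusion.** The point holds for the tables as shelled, in both cohorts. The pooled percentage depends on case mix, its denominator is unclear, and it shows neither how step-down went nor how patients did after failure or modification. The direction requires only that step-down patients do better than the others.

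A reader might go further and conclude that the tables will overstate rescue response by a known amount. The documents give no rate of follow-on antibiotic use and no response rate for either group. In the illustration the excess over r is w × (0.95 − r), which runs from 0.2 × 0.25 = 5 points to 0.8 × 0.45 = 36 points. That range comes from the assumed inputs and is not an estimate.

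Nor does the point touch the proportion responding to Zinforo (Objective 3), which does not draw on these tables. This is a reporting weakness in a descriptive endpoint, worth correcting because the remedy is simple.

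**What to change.** In Tables 28 and 55:
- Use as denominator the patients who received a post-Zinforo antibiotic for the index infection, and print that N.
- Show two columns: Zinforo responders; and Zinforo non-responders or patients with treatment modification. Build them from the CRF response item and the failure and modification reasons. Say that modification takes precedence where both apply, because a switch for non-susceptibility is a modification in SAP 5.1.4 but is not among the failure reasons in SAP 5.1.2.
- Show counts in the second column even if it does not exceed 30 patients, and record this as an exception to SAP 4.1.4.

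The responder/non-responder layout already exists in Tables 10, 11, 37 and 38, so the cost is shell wording and a small amount of programming.

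Optionally, add a level for improvement, oral step-down or de-escalation to the switch reasons in Tables 27 and 54. If the eCRF can no longer be changed, derive it from the route, oral-switch and de-escalation data, provided that these were captured.

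The downside is a small second column, in the tens of patients per cohort, with imprecise percentages.

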8.1.8 ANALYSES OF CSSTI PATIENTS

8.1.9 PATIENT CHARACTERISTICS IN PATIENTS WITH CSSTI

Table 29. Demographic characteristics of included cSSTI patients at index hospitalization

Demographic characteristics	All cSSTI patients (N=XX)	
	n	%
Age		
<90 years		
≥ 90 years		
If <90 years,		
Mean (SD)		
Median (Min Max)		
<65 years		
≥ 65 years		
Sex		
Male		
Female		
Race, Ethnicity		
White, Caucasian		
Black/African-American/Caribbean		
Latin-American		
Asian		
Middle Eastern		
Mixed		
Other		
Not available		
Country		
France		
Greece		
Italy		
Spain		
Russia		
Brazil		
Columbia		
Mexico		
Height (cm)		
Mean (SD)		
Median (Min-Max)		
Unknown		
Weight (kg)		
Mean (SD)		
Median (Range)		
Unknown		
BMI		
Mean (SD)		
Median (Min-Max)		

PFIZER CONFIDENTIAL

CCI

Demographic characteristics	All cSSTI patients (N=XX)	
	n	%
Unknown		
Type of residence/cohabitation (pre index if changed after discharge)		
Nursing home or extended care facility		
Living independently		
Living with care support (family, friend, hired support)		
Other		
Unknown		
Smoking habits		
Non-smoker		
Ex-smoker (stopped \geq 365 days ago)		
Occasional smoker (less than 1 tobacco product per day)		
Habitual smoker (1 or more tobacco products per day)		
Unknown		

Abbreviations: Max: maximum; Min: minimum; SD: Standard deviation

PFIZER CONFIDENTIAL

CCI

Table 30. Medical history in patients with cSSTI

Medical history	All cSSTI patients (N=XX)	
	n	%
Medical condition(s) the patient presented at index visit hospitalization		
None		
AIDS/HIV infection		
If HIV infected: Controlled with HAART		
Yes (n, % HIV infected)		
No (n, % HIV infected)		
Unknown (n, % HIV infected)		
Alcohol abuse		
Cancer/malignancy		
Cerebrovascular disease		
Chronic dialysis within the past 30 days		
Chronic obstructive pulmonary disease		
Chronic renal disease		
Congestive heart failure		
Decompensated cirrhosis		
Diabetes mellitus		
Immunosuppressive disease		
Influenza		
Injection drug use		
End stage liver disease		
Peripheral vascular disease		
Respiratory disease		
Other relevant condition(s) or disease(s) requiring chronic drug treatment.		
Unknown		

Abbreviations: AIDS/ HIV acquired immunodeficiency syndrome/ human immunodeficiency virus, HAART highly active antiretroviral therapy.

Table 31. Hospitalization and treatments in the 3 months prior to index hospitalization in patients with cSSTI

Prior hospitalization	All cSSTI patients (N=XX)	
	n	%
Hospitalization for any reason in the 3 months before index hospitalization		
Yes		
No		
Unknown		
If hospitalized		
Duration of Hospitalization previous to index		
Mean (SD)		
Median (Min-Max)		
Invasive major surgical treatment in the 3 months before index		
Yes		
No		
Unknown		
Therapies received in the 3 months before index		
Antimicrobial (e.g. antibiotics, antivirals)		
Immunosuppressors/ immunomodulators		
Anticoagulants		
Non-steroid anti-inflammatory agents (NSAIs)		
Home infusion therapy		
Home wound care provided by a medical professional		
None		

Abbreviations: Max: maximum; Min: minimum; SD: standard deviation.

Table 32. cSSTI Characteristics

Characteristics	All cSSTI patients (N=XX)	n	%
Lesions involved in the patient's cSSTI			
Abscess			
Cellulitis/fasciitis			
Post-traumatic wound			
Post-surgical wound			
Decubitus ulcer			
Diabetic leg ulcer			
Peripheral vascular disease ulcer			
Burn			
Bite			
Unknown			
None of the above			
Body areas involved in cSSTI			
Head			
Hand			
Upper extremities			
Lower extremities			
Thorax			
Abdomen			
Genitalia			
Unknown			
Muscle			
Unknown			
Extension of the skin infection (cm²)			
<5 cm ²			
5-10 cm ²			
10-50 cm ²			
>50 cm ²			
Unknown			
Level of infection			
Superficial			
Deep incisional			
Organ or space infection			
Unknown			
Anatomical structures affected			
Epithelium			
Epidermis			
Dermis			
Subcutaneous fat			

PFIZER CONFIDENTIAL

CCI

Characteristics	All cSSTI patients (N=XX)	
	n	%
Fascia		
Muscle		
Unknown		

PFIZER CONFIDENTIAL

CCI

Table 33. Diagnosis and infection details in patients with cSSTI

Characteristics	All cSSTI patients (N=XX)	n	%
Time of cSSTI diagnosis			
Prior to index hospitalization			
Days prior to index hospitalization			
Mean (SD)			
Median (Min-Max)			
During index hospitalization			
Days prior after hospitalization (admission)			
Mean (SD)			
Median (Min-Max)			
Unknown			
Recurrent cSSTI infection			
Yes			
No			
Unknown			

Abbreviations: Max: maximum; Min: minimum; SD: standard deviation.

Table 34. cSSTI Diagnostics

Diagnostic criteria	All cSSTI patients (N=XX)	
	n	%
Triggering signs and symptoms for cSSTI at diagnosis		
Purulent or seropurulent drainage/discharge		
Bullae		
Erythema		
Fluctuance		
Heat/localized warmth		
Pain/tenderness to palpitation		
Swelling/induration		
Skin necrosis		
Systemic signs of cSSTI at diagnosis		
Temperature > 38°C		
White blood cell count > 10,000/mm ³ or < 4,500/mm ³ or immature neutrophilis >10%		
Septic shock		
Organ dysfunction		
Unknown		
None of the above		
Tests conducted for cSSTI diagnosis		
Blood cultures		
Superficial swab and culture		
Needle aspiration		
Skin biopsy		
Surgical sample		
X-ray		
Ultrasound		
CT/MRI		
Unknown/not performed		
Microbiological cSSTI diagnosis positive for		
Methicillin resistance Staphylococcus aureus		
Methicillin susceptible S. aureus (MSSA)		
Staphylococcus coagulase negative		
Vancomycin Intermediate S. aureus (VISA)		
Streptococcus pneumonia		
Multidrug resistant S. pneumoniae (MDRSP)		
Penicillin resistant S. pneumoniae (PRSP)		
Beta-hemolytic Streptococci		
Streptococcus pyogenes		
Streptococcus agalactiae		
Enterococcus faecalis		
Enterococcus faecium		
Gram-negative bacilli		
Non-fermenting enterobacteria		

PFIZER CONFIDENTIAL

CCI

Diagnostic criteria	All cSSTI patients (N=XX)	
	n	%
Clostridium spp.		
Other strict anaerobic bacteria		
Other microorganism		
Mixed flora		
Unknown		
None of the above		

PFIZER CONFIDENTIAL

CCI

